#### **8.3.1.2.1.3. One Touch Stockings of Cambridge (OTS - MLC)**

One Touch Stockings of Cambridge is a computerized test of executive function. For this task, participants must stack a set of colored balls to match an example by moving 1 ball at a time into 1 of 2 possible locations. The goal is to perform the task using the smallest number of moves possible. The primary measure for analysis is time to 1st correct response.

The OTS test will be assessed on Screening Period (Day -28 to -2 and Day -1), Day 14, Day 28, Day 84, and Day 112.

#### **8.3.1.2.1.4. Paced Tapping Test (PTAP)**

In Paced Tapping, examinees are presented with auditory pacing tones and instructed to harmonize their fingertaps with the pacing tones. A self-paced phase follows, in which the auditory pacing cue is removed, and ends with another auditory cue demarking the end of the test. The primary measure of analysis is paced tapping consistency, calculated as 1/SD of the intertap interval (1/sec).

The PTAP test will be assessed on Screening Period (Day -28 to -2 and Day -1), Day 14, Day 28, Day 84, and Day 112.

#### **8.3.1.2.1.5. Huntington's Disease Everyday Functioning (Hi-DEF) – at Home Subdomain Score**

The Hi-DEF Scale is a self-reported measure to capture difficulties experienced in daily life due to HD across four different areas of functioning. The key secondary outcome will consider Home subdomain assessment. More detail about Hi-DEF and how these scores should be calculated are presented in Section [8.3.1.3.10.1](#).

The Hi-DEF will be assessed on Screening Day -1, [REDACTED] Day 84, [REDACTED].

#### **8.3.1.2.1.6. Clinical Global Impression – Severity (CGI-S) – Cognitive Status Subdomain score**

[figure not shown]
The CGI-S scale is a validated instrument developed by the National Institute of Mental Health specifically for use in clinical studies. Cognitive Status Subdomain is one of clinical global impression severity scales domains, for which clinicians generate ratings of the severity of the participant's condition over the past 7 days (including the day of the clinic visit) ([Guy 1976, Busner 2007](#)). Please see Section [8.3.1.3.12](#) for more details.

The CGI-S test will be assessed on Screening Period (Day -28 to -2 and Day -1), [REDACTED] Day 84, [REDACTED].

### 8.3.1.3.

Term	Percentage
GMOs	85%
Organic	80%
Natural	75%
Artificial	55%
Organic	80%
Natural	75%
Artificial	55%
Organic	80%
Natural	75%
Artificial	55%
Organic	80%
Natural	75%
Artificial	55%

**Table 2.** [REDACTED]

8.3.1.3.1. [REDACTED]

[REDACTED]

8.3.1.3.2. [REDACTED]

[REDACTED]

[REDACTED]

[REDACTED]

[REDACTED]

[REDACTED]

8.3.1.3.3. [REDACTED]

[REDACTED]

8.3.1.3.4. [REDACTED]

8.3.1.3.5. [REDACTED]

[REDACTED]

8.3.1.3.6. [REDACTED]

[REDACTED]

[REDACTED]

[REDACTED]

[REDACTED]

#### **8.3.1.3.7. The Unified Huntington's Disease Rating Scale UHDRS**

The Unified Huntington's Disease Rating Scale (UHDRS) was developed as a multi-domain clinical rating scale for assessment of functional capacity in HD. Select scales of UHDRS Part V (Independence Examination) will be administered in this study as described above. Note that the Independence Examination constitutes a Key Secondary Endpoint assessment.

8.3.1.3.7.1. [REDACTED]

8.3.1.3.7.2. [REDACTED]

8.3.1.3.8. [REDACTED]

8.3.1.3.8.1. [REDACTED]

8.3.1.3.8.2. [REDACTED]

8.3.1.3.8.2.1. [REDACTED]

A horizontal bar chart illustrating the distribution of 1000 random numbers. The x-axis represents the value of the random numbers, ranging from 0 to 1. The y-axis represents the frequency of each value, with 100 bars displayed. The distribution is approximately uniform, with most values falling between 0.4 and 0.6. The bars are black and have thin white outlines.

### 8.3.1.3.8.2.2.

A horizontal bar chart illustrating the distribution of 1000 random numbers generated between 0 and 1. The x-axis represents the value of the random numbers, ranging from 0 to 1. The y-axis represents the frequency of each value, with 1000 bars. The distribution is approximately uniform, with most values falling between 0.4 and 0.6. The bars are black and have thin white outlines.

A horizontal bar chart consisting of 15 black bars of varying lengths. The bars are arranged in a grid pattern, with some bars being significantly longer than others. The lengths of the bars correspond to the values in the following table:

Series	Value
1	100
2	95
3	90
4	85
5	80
6	75
7	70
8	65
9	60
10	55
11	50
12	45
13	40
14	35
15	30

### 8.3.1.3.8.2.3.

A horizontal bar chart consisting of 20 black bars of varying lengths. The bars are arranged in two groups: a top group of 5 bars and a bottom group of 15 bars. The bars in the bottom group are preceded by a small black vertical tick mark.

### 8.3.1.3.8.2.4.

A solid black rectangular redaction box, likely used to obscure sensitive information in a document.

[REDACTED]

[REDACTED]

[REDACTED]

[REDACTED]

■ [REDACTED]

■ [REDACTED]

[REDACTED]

■ [REDACTED]

■ [REDACTED]

■ [REDACTED]

■ [REDACTED]

**8.3.1.3.8.2.5.** [REDACTED]

■ [REDACTED]

■ [REDACTED]

[REDACTED]

■ [REDACTED]

A horizontal bar chart consisting of five solid black horizontal bars of increasing length from left to right. The bars are separated by small gaps. The lengths of the bars correspond to the values 1, 2, 3, 4, and 5, arranged from left to right.

A thick black horizontal bar, likely a redacted section of text.

### 8.3.1.3.9.2. [REDACTED]

[REDACTED]

### 8.3.1.3.9.5.

### 8.3.1.3.9.6.

Term	Percentage
GMOs	85%
Organic	75%
Natural	72%
Artificial	65%
Organic	88%
Natural	85%
Artificial	78%
Organic	92%
Natural	88%
Artificial	75%
Organic	90%
Natural	85%
Artificial	70%
Organic	88%
Natural	82%
Artificial	68%
Organic	95%
Natural	90%
Artificial	78%

[REDACTED]

8.3.1.3.10. [REDACTED]

8.3.1.3.10.1. [REDACTED]

8.3.1.3.10.2. [REDACTED]

[REDACTED]

[REDACTED]

[REDACTED]

[REDACTED]

[REDACTED]

### 8.3.1.3.10.3.]

### 8.3.1.3.11.

### 8.3.1.3.11.1.

[REDACTED]

8.3.1.3.11.2. [REDACTED]

### 8.3.1.3.11.4.

### 8.3.1.3.12. Clinician-Rated Outcomes of Symptomatology

### 8.3.1.3.12.1. Clinical Global Impression Severity (CGI-S)

The CGI-S [REDACTED] scales are validated instruments developed by the National Institute of Mental Health specifically for use in clinical studies. For clinical global impression severity scales, clinicians generate ratings of the severity of the participant's condition over the past 7 days (including the day of the clinic visit) (Guy 1976, Busner 2007). These scales will be administered at Baseline and at the end of treatment. [REDACTED]

The CGI-S will be assessed on Screening Period (Day -28 to -2 and Day -1), [REDACTED] Day 84,

The key outcome measure is a single score of:

- CGI-S: Cognitive Status

8.3.1.3.13. [REDACTED]

**8.3.2. Analysis Visit Windows for Efficacy Analyses**

In the analysis of efficacy endpoints data from multiple visits will be used. The scheduled visits will not be windowed and will be used at nominal visit value for treatment period (Days 14, 28, 56 and 84). Unscheduled and early termination (ET) visit will be mapped to a scheduled visit for analysis. Unscheduled measurements and early termination visit will be included only if a scheduled measurement is not available, and if the unscheduled measurement falls within the visit window for the scheduled visit. If there are two or more measurements in a visit window, the measurement taken closest to the study day target will be used in analysis. If the two have same distance from the target study day, the latter one will be used.

**Table 3.** [REDACTED]

**Table 4. Analysis Visit Windows for UHDRS – Independence Scale, Hi-DEF, [REDACTED] CGI-S, [REDACTED]**

Scheduled Visit	Study Day of Expected Visit	Study Day Window for Visit
Baseline	1	$\leq 1$
Day 84 ( $\pm 2$ days)	84	57 to 98

**Table 5. [REDACTED]**

[REDACTED]

**Table 6. [REDACTED]**

[REDACTED]

**Table 7. Analysis Visit Windows for MoCA**

Scheduled Visit	Study Day of Expected Visit	Study Day Window for Visit
Baseline	Day -28 to -2	$\leq 1$

### 8.3.3. Analysis of Primary Efficacy Variable

The FAS will be used for all efficacy summary tables. Participants will be analyzed according to randomized treatment.

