## 5.2. Sample Size and Study Power

The study is designed to detect a difference between placebo and the SAGE-718 group in the change from baseline to Day 84 for the primary endpoint, SDMT score. Using a 2-sided test at an alpha level of 0.05, a sample size of approximately 71 evaluable participants per treatment group would provide 90% power to detect a difference of 4 points between SAGE-718 and placebo arms in the change from baseline to Day 84 in SDMT values, assuming that the SD of the change from baseline in SDMT is 7.3 points.

Assuming a 20% dropout and a 1:1 randomization ratio, approximately 178 randomized participants (89 per treatment group) will be required to obtain 71 evaluable participants per treatment group. Evaluable participants are defined as those randomized participants who receive IP and have a valid baseline and at least 1 postbaseline SDMT assessment.

Additional participants may be randomized to ensure a sufficient number of evaluable participants or if the dropout rate is higher than 20%.

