## 7. ANALYSIS SETS

### 7.1. Full Analysis Set

The Full Analysis Set (FAS) is defined as all randomized participants who initiate IP and have baseline and at least 1 post-baseline efficacy evaluation. FAS will be used to analyze the efficacy data (participants will be analyzed according to the treatment group randomized to).

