#### 8.3.3.1. Primary Analysis and Estimand

The estimand for the primary efficacy analysis is defined as follows:

- 1) The treatment regimen for participants is placebo or SAGE-718 for 84 days.

- 2) The target population is adult participants with premanifest or early manifest HD.
- 3) The variable of interest is the change from baseline to Day 84 in Symbol Digit Modalities Test (SDMT)
- 4) The intercurrent events could be:
  - a) The premature discontinuation of treatment for any reason. The treatment policy strategy will be used.
  - b) Taking certain medications including, but not limited to, medications with potent effects at the NMDA receptor, including memantine, amantadine, ketamine, or related compounds or other medications, given at doses, frequencies, or in combinations that are likely, in the opinion of the investigator, to have a deleterious effect on cognitive performance, or prescribed cannabis or other THC-containing substances. The treatment policy strategy will be used.

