### 8.3.3.2. Sensitivity Analysis of Primary Endpoint

Sensitivity analysis is planned if >5% of participants in any treatment group have missing data in the primary endpoint or the values could not be used due to the use of prohibited medications.

If any of the sensitivity analyses yields a result that is in a different direction from the result of the primary analysis, the nature of the discrepancy will be examined to clearly explain the discrepancy based on statistical principles and the discrepancy will be discussed in the CSR.

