#### 8.3.3.2.2. Control-Based Pattern Mixture Model Multiple Imputation (PMM-MI)

- A sensitivity analysis using control-based Pattern Mixture Model Multiple Imputation (PMM-MI) under the missing not at random (MNAR) assumption will be used to investigate the impact of missing data ([Lingling 2019, SAS Institute Inc.](#)). MNAR assumes the missingness depends on the unobserved study data and cannot be predicted solely based on participant's observed data.

Control-based PMM-MI under MNAR involves four steps as described below.

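### The control-based imputation and tipping-point analyses run in the FAS, so dosed participants with a baseline SDMT but no post-baseline efficacy evaluation fall outside them

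*SAP*

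**What the plan says.** **Analysis set.** SAP 7.1 limits the FAS to randomised participants who started IP and "have baseline and at least 1 post-baseline efficacy evaluation". Section 8.3.3, which contains the sensitivity analyses, opens with "The FAS will be used for all efficacy summary tables". Neither 8.3.3.2.2 nor 8.3.3.2.3 names another set, and 8.3.3.3 rules out sensitivity runs on the (redacted) supportive set.

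**Purpose.** The control-based imputation "will be used to investigate the impact of missing data". The tipping point examines departures from missing at random. Both serve an estimand whose first intercurrent event reads: "The premature discontinuation of treatment for any reason. The treatment policy strategy will be used" (SAP 8.3.3.1). The same strategy is assigned there to the use of listed medications.

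**Trigger.** SAP 8.3.3.2 starts the sensitivity analyses when more than 5% of a group has missing primary endpoint data, or when "the values could not be used due to the use of prohibited medications".

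**Code.** SAP Appendix B codes y1 to y3 as Days 14, 28 and 84. Baseline is in the variable list of Step 2 (making the pattern monotone). It is absent from the control-based Step 3 (`var y1 y2 y3`) and from the tipping-point macro (`var trtp y1 y2 y3`).

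**The concern.** A participant with a baseline only adds nothing to an MMRM on change from baseline, so the FAS costs the primary analysis nothing in this respect. Imputation is different: it can give such a participant a Day 84 value under a stated assumption. People who take IP and leave before any assessment are the most complete form of missing data, and treatment policy covers discontinuation for any reason. Leaving them out means the stress tests examine only the milder missingness. If early loss were higher on SAGE-718, the control-based estimate would be larger, and the tipping point further away, than if all dosed participants were included.

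The medication wording raises a smaller issue. Under treatment policy, taking a listed medication does not make an SDMT value unusable, yet the trigger is phrased as if it could.

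**Working it through.** **1. The plan's own figures.** SAP 5.2 states that "a sample size of approximately 71 evaluable participants per treatment group would provide 90% power". Its inputs are a two-sided 0.05 level, a true difference of 4 SDMT points and SD 7.3.
- Normal approximation: n = 2 × 7.3² × (1.960 + 1.282)² / 4² ≈ 70 per arm. The noncentral t gives 90.0% power at 71. The figure reproduces.
- Dropout: 71 / 0.80 = 88.75, so 89 per arm and 178 in total. 178 − 142 = 36 (18 per arm) is the whole allowance for non-evaluable participants.

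**2. Who is left out.** The first scheduled post-baseline SDMT is Day 14 (SAP 8.3.1.1). Someone dosed who leaves with no post-baseline efficacy evaluation of any kind is outside the FAS, and so outside 8.3.3.2.2 and 8.3.3.2.3.

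**3. Effect on the control-based estimate.** Let p be the share of dosed SAGE-718 participants with no post-baseline data. Imputed from placebo, they carry about zero benefit. Placebo participants imputed from placebo leave their arm's mean about unchanged. So:

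estimate (all dosed) ≈ (1 − p) × estimate (FAS)

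This was compared with a simulation: 500 trials per setting, 89 per arm, true effect 4, 15% later dropout, placebo-based sequential regression with baseline, 10 imputations, Rubin pooling, Day 84 ANCOVA. The early shares are assumptions.

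| No post-baseline data (placebo / SAGE-718) | FAS | (1 − p) × FAS | Simulated, all dosed | Fall |
|---|---|---|---|---|
| 3% / 3% | 3.63 | 3.63 × 0.97 = 3.52 | 3.52 | 0.11 (3.0%) |
| 5% / 5% | 3.63 | 3.63 × 0.95 = 3.45 | 3.46 | 0.17 (4.7%) |
| 2% / 8% | 3.62 | 3.62 × 0.92 = 3.33 | 3.33 | 0.29 (8.0%) |

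For scale, the standard error at 71 per arm is 7.3 × √(2/71) = 1.22, so the largest fall is about a quarter of a standard error.

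**4. Ceiling.** If all 18 per arm were of this kind and there were no later dropout, the estimate would be 4 × 71/89 = 3.19.

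**5. Tipping point.** The SAP text shifts imputed SAGE-718 values by δ. The direct Day 84 shift in the arm mean is q × δ, where q is the share imputed. Assume 15% later dropout among FAS members, and take δ = −3, the end of the range in 8.3.3.2.3.
- FAS: 0.15 × (−3) = −0.45.
- All dosed, p = 3%: q = 0.03 + 0.97 × 0.15 = 0.176, shift −0.53.
- All dosed, p = 8%: q = 0.08 + 0.92 × 0.15 = 0.218, shift −0.65.

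The same δ therefore tests less in the FAS.

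**6. Why a filter alone is not enough.** A baseline-only participant already fits a monotone pattern, so Step 2 has nothing to fill in. Step 3 and the tipping-point macro then work from lists in which this participant has no observed SDMT value. Their one measurement would be ignored.

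**7. Medication wording.** SAP 8.3.3.1 keeps values after the listed medications. The second limb of the trigger in 8.3.3.2 presupposes that some are not usable. Protocol 13.2 triggers on missing data alone, so the limb is specific to the SAP. No visible passage says when a value becomes unusable, and no step in 8.3.3.2.1 to 8.3.3.2.3 sets one to missing.

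**The case against.** **Few people are affected.** This stands. The FAS asks for any efficacy evaluation, not an SDMT, so some participants without a post-baseline SDMT remain in it. Those who stop IP are asked to keep attending (Protocol 8.4). Those who leave are asked for an early termination visit (Protocol 8.4.1, 8.4.2), which SAP 8.3.2 maps to a scheduled visit when it falls in the window; the window table that would cover the SDMT cannot be seen. The loss is mainly people who leave before Day 14 and also miss that visit. Nothing in the documents supports a particular share, or a higher one on SAGE-718.

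**The size restates the assumption.** This also stands. The fall is close to p by construction, and the simulation only confirms the algebra. In a separate simulation (400 trials per setting, assumed visit correlations, baseline in the model) the shift was 0.12 to 0.30 points, and 3 to 4% of trials lost a significant FAS result. Without baseline, 7 to 13% did, partly from added noise.

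**Keeping one set isolates the missing-data assumption**, which helps the forest plot in SAP 8.3.3.3. That is a fair reason to show the FAS version as well. It does not justify leaving the most incomplete cases out of every stress test.

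**The medication clause is only a trigger.** Correct. A reader might infer that the SAP orders values after such medication to be deleted; it does not. SAP 8.2.2 refers exclusion of affected data to a Protocol Deviation Specification that is not available here.

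**Conclusion.** The point holds as a modest gap. Two analyses meant to probe missing data omit dosed participants with a baseline SDMT and no post-baseline efficacy evaluation. The fall of 0.1 to 0.3 points rests on assumed active-arm shares of 3 to 8% and on placebo-based imputation giving those participants no benefit.

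Three stronger readings are not supported:
- **That 36 participants would be lost.** That number is the entire dropout allowance. It can include people never dosed or without a valid baseline, and people the FAS would still admit through another efficacy measure. It is a ceiling, not an estimate.
- **That the FAS version is too favourable against the truth.** In the simulation the true effect is 4, and both control-based versions lie below it. The FAS version is only less severe than the all-dosed version.
- **That the primary result is biased by this.** The MMRM could not use these participants in any case.

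The medication clause is a wording conflict between 8.3.3.2 and 8.3.3.1. By itself it does not show that data will be removed.

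**What to change.** 1. In SAP 8.3.3.2.2 and 8.3.3.2.3, state that the analysis includes all randomised participants who took IP and have a baseline SDMT, with all their missing SDMT values up to Day 84 imputed. Keep the primary MMRM in the FAS.
2. In Appendix B, add baseline SDMT to the variable lists of the control-based Step 3 and the tipping-point macro, so that baseline-only participants are imputed from their observed value.
3. Reconcile the trigger in 8.3.3.2 with 8.3.3.1: either delete the medication limb, or state that values after such medication are retained.

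The cost is a dataset filter, a small code change and a few sentences. The sensitivity estimates will be slightly less favourable and slightly less precise. Deleting the medication limb also narrows the trigger a little. Settle this before Part 1 of the database lock: a restricted sponsor team is unblinded after it (SAP 5.4), and a later change of set could look data-driven.

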#### 8.3.3.1. Primary Analysis and Estimand

The estimand for the primary efficacy analysis is defined as follows:

- 1) The treatment regimen for participants is placebo or SAGE-718 for 84 days.

- 2) The target population is adult participants with premanifest or early manifest HD.
- 3) The variable of interest is the change from baseline to Day 84 in Symbol Digit Modalities Test (SDMT)
- 4) The intercurrent events could be:
  - a) The premature discontinuation of treatment for any reason. The treatment policy strategy will be used.
  - b) Taking certain medications including, but not limited to, medications with potent effects at the NMDA receptor, including memantine, amantadine, ketamine, or related compounds or other medications, given at doses, frequencies, or in combinations that are likely, in the opinion of the investigator, to have a deleterious effect on cognitive performance, or prescribed cannabis or other THC-containing substances. The treatment policy strategy will be used.
- 5) The population summary level deals with the difference between SAGE-718 and placebo treatments in mean change from baseline to Day 84 in Symbol Digit Modalities Test (SDMT) The primary efficacy endpoint is the change from baseline to Day 84 on the SDMT score. This primary endpoint will be analyzed using a mixed-effects model for repeated measures (MMRM). The model will include baseline SDMT score as a continuous explanatory variable, treatment, assessment time point, and time point-by-treatment as categorical explanatory variables. The Kenward-Roger correction to degrees of freedom will be applied. All explanatory variables will be treated as fixed effects in the model. All post-baseline time points will be included in the model. An unstructured (UN) covariance matrix with the default Newton-Raphson optimization algorithm as implemented in the SAS procedure PROC MIXED will be used to estimate the within-subject correlation. If this model fails to converge, the Fisher Scoring algorithm (via the SCORING option of the PROC MIXED statement), the no-diagonal factor analytic structure (via the TYPE=FA0( $T$ ) option of the REPEATED statement, where  $T$  is the total number of time points), Toeplitz, Autoregressive (1) [AR (1)], Compound symmetry (CS) covariance structure will be used, following this sequence until convergence is achieved. If the model still does not converge with CS structure, the Glimmix procedure with option of parametrizing UN to Cholesky root matrix will be used and in the case it also does not converge no results will be reported. When the covariance structure is not UN, the sandwich estimator for the variance-covariance matrix will be derived, using the EMPIRICAL option in the PROC MIXED statement in SAS. The primary comparison will be between SAGE-718 and placebo at the Day 84. Least squares means and 95% confidence interval will be summarized, and the p-value from the hypothesis test of no difference between the treatment groups will be also presented.

A plot showing the LS means of SDMT score  $\pm$  SE bar over time within each treatment group will be provided.

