### **8.4.2. Early Termination from the Study**

At the time of study withdrawal/stopping study participation, if possible, an ET visit should be conducted. The participant will be permanently discontinued both from the IP and from the study at that time.

If the participant withdraws consent for disclosure of future information, the sponsor will retain and continue to use any data collected before such a withdrawal of consent.

If a participant withdraws from the study, he/she may request destruction of any samples taken and not tested, and the investigator must document this in the site study records.

Possible reasons for study discontinuation include but are not limited to the following:

- AE
- Pregnancy
- Protocol deviation
- Non-compliance with study drug
- Lost to follow-up
- Withdrawal by subject
- Screen failure
- Study terminated by sponsor
- Physician decision
- Other

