#### 8.3.3.2.1. Complete Data Analysis

A sensitivity analysis using only participants who have at least baseline and Day 84 values will be performed. The MMRM analyses proposed for the analysis of the primary outcome will be provided for change from baseline to Day 84. A plot showing the LS mean  $\pm$  SE bar over time within each treatment group will be provided.

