### 8.3.3.2.3. Tipping Point Analysis

Another sensitivity analysis – tipping point analysis will be considered to investigate the robustness of the result to departures from the missing at random (MAR) assumption of the MMRM model and to identify the tipping point where the treatment effect in participants with missing data overturns the treatment effect from statistically significant to statistically non-significant.

Hence the tipping point analysis will only be performed if the primary efficacy analysis is statistically significant in treatment effect.

Implementing the tipping point approach includes the following steps ([Yuan 2014, SAS Institute Inc.](#)):

- 1) Under the MNAR assumption, missing SDMT scores up to Day 84 will be imputed using PROC MI under MNAR.
- 2) The imputed values for observations in SAGE-718 treatment group will be adjusted directly using the shift parameter ( $\delta$ ).
- 3) The imputed datasets with the shift parameter applied will be analyzed using PROC MIXED.
- 4) The results will be combined for the inference using PROC MIANALYZE.
- 5) Step 1-4 will be repeated until the result is not statistically significant.
- 6) If needed, step 1-5 will be repeated with more stringent shift parameter applied until the result is not statistically significant.

The shift parameter ( $\delta$ ) value will start from 0 and decrease by 0.2 decrements until non-significant p-value is achieved. One hundred datasets will be generated.

The tipping point summary for each pairwise comparison will include LSmeans difference, the 95% CI, and p-value for each of  $\delta$  value. From  $\delta = (-3, 0)$ , iterations including the tipping point will be summarized.

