#### Step 3. Generation of imputed datasets for AVAL using control-based pattern imputation under MNAR

```
proc mi data=mono seed=xxx n impute=m outs=imputed;
  min=.. x x x;
  max=.. y y y;
```

```
by _imputation_;  
class trtp;  
var y1 y2 y3;  
monotone reg(/details);  
mnar model(y1 y2 y3/ modelobs=(trtp='Placebo')); *only control group is used to  
derive the imputation model;  
run;
```

Step 4-1. Calculate CHG14, CHG28, and CHG84.

Step 4-2. Convert datasets into long format in which CHG variable represents all change  
from baseline with different values of avisit.

Step 5. Conducting model-based analysis using each imputed dataset

```
proc mixed data= imputed;  
by _imputation_;  
class subjid trtp(ref='Placebo') avisitn;  
model chg = trtp base avisitn trtp*avisitn / ddfm=kenwardroger;  
repeated avisitn / subject=usubjid type=UN;  
lsmeans trtp*avisitn / diff=all cl alpha=0.05;  
ods output lsmeans=lsmeans diff=diffs;  
run;
```

Step 6. Pooling the results from the imputed *m* datasets for inference

```
proc sort data=lsmeans;  
by trtp avisitn _imputatoin_;  
run;  
  
proc mianalyze parms=lsmeans;  
modeleffects estimate;  
ods output ParameterEstimates=lms;  
by treatment avisit;  
run;
```

```
proc sort data=diffs;  
by avisit _imputatoin_;  
run;  
  
proc mianalyze parms=diffs;  
modeleffects estimate;  
ods output ParameterEstimates=dif;  
by avisit;  
run;
```

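### The primary estimand is treatment policy, but the MAR MMRM, and possibly its planned checks, do not target study leavers' off-drug Day 84 outcome; an estimand-matched sensitivity estimate should be added

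*SAP*

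**What the plan says.** **Estimand.** SAP 8.3.3.1 (and Protocol 13.5) lists as an intercurrent event: "The premature discontinuation of treatment for any reason. The treatment policy strategy will be used".

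**Primary analysis.** The same SAP section states: "This primary endpoint will be analyzed using a mixed-effects model for repeated measures (MMRM"). The terms are baseline SDMT, treatment, visit and treatment-by-visit. SAP 8.3.3.2.3 speaks of "departures from the missing at random (MAR) assumption of the MMRM model", so the assumption is acknowledged.

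**Who has no Day 84 value.** Protocol 8.4 and 8.4.1 and SAP 5.1 ask people who stop IP to keep attending visits. For those who leave the study, Protocol 8.4.2 says: "The participant will be permanently discontinued both from the IP and from the study at that time". Under SAP 8.3.2 an early-termination score can stand in for a missed visit if it falls in the window; the window table that would apply to SDMT is not visible.

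**Planned checks, if more than 5% are missing in either arm (SAP 8.3.3.2).**
- Completers: "A sensitivity analysis using only participants who have at least baseline and Day 84 values will be performed".
- Control-based multiple imputation. Step 3 of the sample code in Appendix B contains "mnar model(y1 y2 y3/ modelobs=(trtp='Placebo". Its variable list is the three post-baseline scores (Days 14, 28 and 84), without baseline.
- Tipping point, run only after a significant primary result and left out of the forest plot (SAP 8.3.3.3).

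**The concern.** Under treatment policy, a leaver's Day 84 value is whatever the SDMT would be off drug. The MMRM answers a different question for that person: what the score would be if they had gone on like observed same-arm participants with similar earlier scores. If the benefit fades after stopping, the estimate and its confidence interval would be labelled treatment policy but lean towards SAGE-718.

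The checks could look reassuring for the wrong reason. The completers analysis removes the leavers and estimates nearly the same contrast. The control-based imputation uses placebo regression coefficients but applies them to the leaver's own raw Day 14 and Day 28 scores, which for someone leaving after Day 28 may already contain the drug gain. SAP 8.3.3.2 asks for explanation only when a sensitivity result points in a different direction, so a smaller effect in the same direction would not prompt any.

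At stake are the size of the reported effect and the claim that it is robust to dropout. The test under no effect at all is not at stake.

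**Working it through.** **Inputs from SAP 5.2.** Difference 4 points, SD of change 7.3, two-sided alpha 0.05, 90% power, 71 evaluable and 89 randomized per arm, 20% dropout. SDMT visits after baseline, up to Day 84: Days 14, 28 and 84 (SAP 8.3.1.1).

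**Inputs assumed, because the documents do not give them.** Share p of participants with no Day 84 value; share k of the effect kept after stopping; correlation ρ between visits; time course of the effect.

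**1. The plan's own figure.** A two-sample t-test with 71 per arm has power 90.0% (70 per arm: 89.6%). 71 / 0.8 = 88.75, so 89 per arm and 178 in all. The plan's numbers reproduce.

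**2. MMRM against treatment policy, no off-drug stayers.** The MMRM targets 4. The policy effect is 4 × [1 − p(1 − k)].

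| p | k | Policy effect | Excess | Above truth |
|---|---|---|---|---|
| 5% | 0 | 3.8 | 0.2 | 5% |
| 10% | 0 | 3.6 | 0.4 | 11% |
| 15% | 0 | 3.4 | 0.6 | 18% |
| 20% | 0 | 3.2 | 0.8 | 25% |
| 20% | 0.5 | 3.6 | 0.4 | 11% |

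In the fourth row, 0.8 is 20% of the MMRM value but 25% of the policy effect. Power at 71 per arm for a 3.2-point effect is 74%.

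**3. Discontinuers who stay.** Suppose 20% stop IP with k = 0, and a share s of them attend Day 84. Observed participants then average 4 × 0.8 / (0.8 + 0.2s). For s = 25%, 50% and 75% this is 3.76, 3.56 and 3.37 against a truth of 3.2: 18%, 11% and 5% too high.

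**4. Control-based imputation as in the sample code.** Take 20% leaving after Day 28, k = 0 and equal correlation ρ between visits. The placebo regression of Day 84 on Days 14 and 28 has coefficient ρ/(1 + ρ) on each.
- *Full effect by Day 14.* A leaver keeps 2ρ/(1 + ρ) of it: 75%, 89% and 95% at ρ = 0.6, 0.8 and 0.9. The estimate is 3.2 + 0.8 × that share = 3.80, 3.91 and 3.96, so 25%, 11% and 5% of the excess is removed.
- *Effect linear to Day 84.* Effects at Days 14 and 28 are 4 × 14/84 = 0.67 and 4 × 28/84 = 1.33. The share kept is (0.67 + 1.33)/4 × ρ/(1 + ρ): 19%, 22% and 24%. The estimate is 3.35, 3.38 and 3.39, so 76-81% of the excess is removed.
- *Baseline added, full effect by Day 14.* The share kept is 2ρ/(1 + 2ρ): 55%, 62% and 64%. The estimate is 3.64, 3.69 and 3.71.

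**5. Choice of remedy.** Large-sample simulation with full effect by Day 14, raw SDMT SD 8 to 14, and correlation set so that the SD of change is 7.3. If dropout is unrelated to outcome, imputing SAGE-718 leavers from placebo given baseline only returns about 3.2, the truth. If instead the worst 20% by Day 28 change leave both arms, that method gives 3.8-4.1, no better than the MMRM at 4.0. Jump to reference, with each leaver's own earlier residuals carried over, gives about 3.2.

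**The case against.** **The 20% is not a Day 84 missing rate.** SAP 5.2 says "Assuming a 20% dropout and a 1:1 randomization ratio, approximately 178 randomized participants (89 per treatment group) will be required" to reach 71 evaluable per arm, and evaluable requires only one post-baseline SDMT. Read literally, those 20% have no post-baseline score and lie outside what the MMRM fills in. A reader might infer that the plan itself implies a 0.8-point overstatement. It does not: p is an assumption, and 0.8 is the top of the range shown. This objection stands in full.

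**Discontinuers are followed.** Nothing removes their off-IP scores, so leavers are predicted from a mixture of on-drug and off-drug outcomes. A reader might infer that the MMRM credits leavers with the whole on-drug effect; that is true only if no discontinuer stays. Early-termination scores inside the window shrink the gap further. This also stands, though nothing in the plan ensures that enough discontinuers stay.

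**The control-based check may work well.** A reader might infer that it removes little in any case. That needs early onset, and the documents give no SDMT time course. Early onset is plausible, since Protocol 5.2 reports cognitive benefit in 14-day studies, but it is not established for SDMT. The code is also headed as a sample, and Steps 1 and 2 of it do include baseline.

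**The tipping point reports estimates.** It gives a difference and confidence interval at each shift. With 20% leavers, a Day 84 shift of −3 gives 4 − 0.2 × 3 = 3.4, close to the worst-case truth. Matching 3.2 would need −4, beyond the −3 to 0 range named for the summary. The analysis is also conditional on significance, and its sample code shifts the placebo arm while the text shifts SAGE-718. It is useful, but it does not replace an estimand-matched estimate.

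**Conclusion.** The mismatch is real and limited. The estimand is treatment policy, the primary model is MAR without IP status, leavers are off IP, and no estimate planned for the forest plot is sure to target their off-drug Day 84 outcome.

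The worst-case excess is 0.2 to 0.8 points for 5% to 20% leavers. It rests on a 4-point on-drug effect, complete loss after stopping and no off-drug stayers, and it shrinks as any of these is relaxed. How much the control-based check recovers depends on onset: little if the effect is full by Day 14, most if it builds towards Day 84. A reader might also infer a false-positive problem; if the drug has no effect on or off treatment, there is no gain to carry forward and the type I error is unaffected. This calls for an added sensitivity estimate, not a new primary analysis.

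**What to change.** Keep the MMRM as the primary test. Before the Part 1 lock, amend SAP 8.3.3.2 and Appendix B as follows.

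1. Replace or supplement the completers analysis with a standard jump-to-reference multiple imputation. For SAGE-718 participants with no Day 84 value after leaving, use the placebo mean profile from the time of leaving, and carry over their own baseline and earlier residuals from the SAGE-718 arm means. Do not impute from baseline alone. Impute missing placebo values under MAR, and keep every observed off-IP value.
2. Add baseline to the Step 3 imputation model of the existing control-based analysis.
3. Show the jump-to-reference Day 84 difference and 95% CI in the forest plot beside the primary result.
4. State that the MMRM estimate assumes leavers would have continued like observed same-arm participants.

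The cost is SAP wording and a little extra programming, with no new data or participants. The downside is that the added estimate will usually be smaller than the MMRM estimate, and it is conservative if some benefit lasts after stopping.
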